	5.3 Statistics	
	5.3.1 Sample size rationale	
6	Quality control and quality assurance	6
7	Ethics	6
8	Finance	6
9	Publication policy	7
10	Time Schedule	7
11	Organization and staff	7
12	References	8

2 Background

Low back pain (LBP), defined as pain and discomfort located below the costal margin and above the inferior gluteal folds, with or without leg pain, is associated with great morbidity and significant socio-economic impact in many parts of the world (1-3). The lifetime prevalence of LBP is reported to be as high as 60-85% and an incidence of 5% per year for adults (1, 4, 5).

The underlying pathophysiologies of LBP are many, diverse and often obscure, including: spinal stenosis, infections, inflammation, tumors, fractures, etc. (6, 7). Intervertebral disc herniation (IDH), more specifically lumbar disc herniation (LDH), is a common cause of LBP, irrespective of whether the disc protrudes into the spinal canal and exerts pressure on the lumbar nerve roots or not (8). It is hypothesized that IDH causes a combination of nerve root ischemia and inflammatory processes leading to neoinnervation and neovascularization, which in turn leads to LBP (8-10).

Studies have shown that most LDH can be treated effectively with conservative management and the passage of time. However for the group of patients where pain and disability is of such magnitude or recovery is unacceptably slow, surgical intervention provides effective clinical relief in many cases (11-13). Despite the immediate and effective relief often provided by surgery, the literature indicates that it has limited superiority over conservative regimes on the long-term outcome of 1-2 years (8, 11, 14, 15). Furthermore, as many as 10-40% of patients report unsatisfactory results of lumbar disc surgery, depending on outcome measures (14, 16, 17).

Due to this relative high number of unsatisfactory operative outcomes, great emphasis should be put on pre-operative investigation and diagnostics in order to find the candidates who will most likely benefit from surgery and simultaneously identify those where other interventions would lead to greater gain. Currently, magnetic resonance imaging (MRI) is considered the imaging procedure of choice for patients suspected of LDH (18-21). However, due to inter-observer variations and the inability to determine the relevance of a pathoanatomical abnormality in relation to clinical symptoms, the need for novel diagnostic tools, in particular imaging, in the selection of operative candidates with IDH remains.

It has been hypothesized that chronic LBP may lead to persistent hyperalgesia (22), which may in turn adversely affect the efficacy of surgery. Several studies have been performed to investigate the nature and extend of hyperalgesia in relation to LBP. The findings have previously been of conflicting character, however more recent research indicate that hyperalgesia is a common finding in chronic LBP, but does not constitute a separate risk factor (22-28). With the increasing availability of functional imaging equipment and novel techniques for monitoring cerebral activity (*f*MRI, PET, SPECT), new diagnostic opportunities may help shed light on the mechanisms leading to chronic pain, subsequent development of generalized hyperalgesia and affecting the outcome of spinal surgery (29).

Unfortunately, structural imaging alone, due to its non-specificity and low sensitivity, is of limited value in this setting. Therefore, there is a dire need for newer approaches that are based on hardcore sciences such as molecular and cellular imaging with PET. The utilization of fMRI-based analysis of pain have been tried and the published data are fairly indefensible, and therefore, new frontiers have to be explored for defining the role of functional imaging in this complicated and disabling source of pain in these patients. Currently there is a lack of data in the literature regarding applications of PET in musculoskeletal disorders, in particular spinal diseases, however previous studies have generated data about the role of PET in assessing the effects of pain in the thalamus (30).

3 Objectives

The objective of this thesis is to investigate whether quantitative sensory testing (QST) of experimental pain responses can predict surgical outcome in patients with LDH.

- Can QST be used to identify patients with a change in pain perception and potential abnormal response to painful stimuli?
- Can QST be used to reflect patients pain perception using self-reported questionnaires on pain?
- Is there a correlation between quantitative sensory testing of experimental pain responses and clinical outcome of surgery in LDH patients assess using standardized questionnaires?

4 Methods

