4.3 Patient course

Patients identified by the attending surgeon as eligible for inclusion (see in- and exclusion criteria previously mentioned) are invited to participate. Patients who express an interest in participating will be given written and oral information on the purpose, nature and implications of study-participation. Information and inclusion of participants will be conducted in accordance with the guidelines of The Health Research Ethics Committee System in Denmark, from which approval will be sought.

Prior to surgery at the Center for Spine Surgery and Research, Middelfart, study subjects will undergo assessment and quantification of pain sensitivity using a standardized QST battery and pain drawing (figure 1). Patients will also be asked to fill-out multiple questionnaires (basic personal information, EQ-5D, OSWESTRY, SF-36, VAS-leg/-back, etc.) as stated in section 5.1 Data collection.

The standardized QST battery consist of 3 different modalities, covering different measurements of pain perception and multiple types of pain stimulus. Initially patients will undergo a simple Pressure Pain Test (PPT) using an electronic/analog pressure pain algometer at the thenar eminence of the hand and the most painful site of the lumbar area, as previously described (25, 32). Patients are instructed to indicate when pain is felt, Pressure Pain Detection Threshold (PPDT). Pain intensity at 140% of PPDT, the Pain Response (PR) is subsequently rated on a VAS. Immediately following both the thenar and lumbar test, a temporal summation test will also be performed. Using a 51,2g PinPrick stimulator, initially a single stimulus will be given, and the patient asked to rate the pain. Thereafter 10 repetitive stimuli will be given and the patient asked to rate the pain of the last stimulus. Temporal summation can then be calculated as the difference in pain following a single stimulus vs the last in a series of 10.

To test for deep mechanic pain sensitivity, a pneumatic double-chamber cuff will be placed around: (i) the arm and (ii) the leg. Cuff inflation rate will be constant and the pain intensity registered continuously on a visual analogue scale (VAS); thresholds of detection and tolerance will be recorded.

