4.4 Facilities

The staff at Center for Spine Surgery and Research, Middelfart will perform initial consultation, assessment, surgery and post-operative treatment.

The Ph.D.-student will perform the initial recruitment and the standardized QST.

5 Data & Statistics

Clinical Tools	At inclusion and pre- operative	6-weeks ambulatory control	6-month ambulatory control	12-month ambulatory control
EQ-5D	х	Х		Х
Oswestry Disability Index (ODI)	х			Х
SF-36	Х			Х
Standardized QST	Х	Х	Х	
VAS-leg and VAS-back	х	Х	Х	X
Pain drawing	х	Х	Х	X
DaneSpine questionnaire		Х		Х

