5.3.1 Sample size rationale

Based on the data gathered during the initial pilot-study, reverse power-calculations have been performed on variables showing tendency towards significance in Spearman's Rank Correlation and Pearson's Correlations. Based on these calculations an estimated study group of 70-100 patients is needed to secure substantial data for statistical significance.

6 Quality control and quality assurance

The study will be registered at the Ethical Committee of Southern Denmark and the Danish Data Protection Agency.

All patient data, including information on private matters or other confidential information, will be strictly confidential and stored according to the Danish Open Administration Act, the Danish Act on Processing of Personal Data and the Health Act.

The study will be performed in accordance with the guidelines recommended by STROBE (STrenghtening the Reporting of OBservational studies in Epidemiology).

7 Ethics

This study will be a clinical trial conducted according to Danish ethical principles as well as the Declaration of Helsinki.

We take the patients' rights into account, as participation in the study is completely voluntary and can only take place after receiving both oral and written information about the study. Furthermore, all participants must sign a consent form. At any time during the study, the participants can withdraw their consent orally, in writing or by any other clear notification. If the participant chooses to withdraw the consent it will not affect the right to any current or future treatment.

The participants are entitled to bring a member of the family or friend to the informative interview and will be given 24 hours to consider participation before signing the consent form. The Informed Consent form will be signed by all participating patients and stored at the Center for Spine Surgery and Research, Middelfart.

According to the Danish Open Administration Act the participants are entitled to access the research protocols and documents concerning the patient's own participation in the study. This opportunity is available for two years after completion of the study.

The patients have the right to complain and apply for compensation according to the Act on the Right to Complain and Receive Compensation within the Health Service.

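### The study is sized for statistical significance, but no primary QST measure, outcome, visit or test is named and nothing controls error across about 75 possible pairs

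*Combined protocol and SAP*

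**What the plan says.** Section 3 sets the aim as to "investigate whether quantitative sensory testing (QST) of experimental pain responses can predict surgical outcome in patients with LDH". The third study question turns this into a correlation: "Is there a correlation between quantitative sensory testing of experimental pain responses and clinical outcome of surgery in LDH patients assess using standardized questionnaires". Neither statement names a measure, scale, visit or definition of surgical success.

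Section 4.3 (Patient course) describes the battery: "The standardized QST battery consist of 3 different modalities". Pressure pain is tested "at the thenar eminence of the hand and the most painful site of the lumbar area". There is also a supra-threshold rating: "Pain intensity at 140% of PPDT, the Pain Response (PR) is subsequently rated on a VAS". A further test is added at both sites: "Immediately following both the thenar and lumbar test, a temporal summation test will also be performed". Cuff thresholds at arm and leg, a cold-pressor test, a repeat of the pressure test to assess conditioned pain modulation (CPM), and a hypertonic saline injection complete the battery.

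The schedule table in section 5 (Data & Statistics) lists EQ-5D, ODI, SF-36 and "VAS-leg and VAS-back" at 12 months, with some of them also at 6 weeks or 6 months.

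Section 5.3 gives frequencies, percentages and descriptive statistics. It contains no test, model, significance level or multiplicity rule. Section 5.3.1 says that the sample size came from pilot "variables showing tendency towards significance in" Spearman and Pearson correlations, and gives 70-100 patients as the number needed for statistical significance. The pilot variables are not named. The contents list shows no other statistics section.

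**The concern.** The plan intends a significance claim without saying which one. With many sensory measures and several questionnaires, the question whether QST predicts outcome can be answered by whichever pair looks best after the data are seen. The correlation reported would then be a selected maximum: its size would be biased upwards and its p-value would not have its nominal meaning. This matters because the Background wants better ways to find the patients most likely to benefit from surgery. A chance association presented as a predictor would work against that purpose.

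**Working it through.** **The plan's own figure.** The 70-100 patients cannot be reproduced, because the correlation, significance level, power and dropout are not given. Assuming two-sided 5% and 80% power, the detectable correlation is r = tanh[(1.960 + 0.842)/√(n − 3)]:
- n = 70: tanh(2.802/√67) = 0.33
- n = 100: tanh(2.802/√97) = 0.28

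**Counting the pairs** (section 4.3 and the section 5 table; pre-operative QST only)

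| QST measure | Count |
|---|---|
| Pressure detection threshold, thenar and lumbar | 2 |
| Pain response, two sites | 2 |
| Temporal summation, two sites | 2 |
| Cuff detection and tolerance, arm and leg | 4 |
| Cold-pressor VAS and withdrawal time | 2 |
| CPM, two sites | 2 |
| Saline VAS | 1 |
| Total | 15 |

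Outcomes at 12 months: EQ-5D, ODI, SF-36, VAS-leg, VAS-back = 5. Pairs: 15 × 5 = 75.

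One CPM index per site and one score per questionnaire are counting choices. If 6 weeks (EQ-5D and two VAS) and 6 months (two VAS) are added, there are 5 + 3 + 2 = 10 outcome-visits and 15 × 10 = 150 pairs. The rest of the working uses 75.

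**False positives with no true association, at an assumed 5%**
- Expected number: 75 × 0.05 = 3.75, whatever the correlation among measures.
- Chance of at least one if the tests were independent: 1 − 0.95^75 = 97.9%.
- With correlated measures: simulation of normal data with equal correlation within the QST set and within the outcome set, none between the sets, each pair tested by Pearson at n = 70 and n = 100. The two sample sizes agree to within about 2 percentage points.

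| Correlation among QST / among outcomes | Chance of at least one false positive |
|---|---|
| 0 / 0 | about 98% |
| 0.3 / 0.5 | 91% |
| 0.5 / 0.6 | 79-81% |
| 0.7 / 0.7 | 60-61% |
| 0.8 / 0.8 | 43-45% |

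**Size of the selected correlation.** At n = 70 the expected largest |r| among 75 null pairs is about 0.31 (independent) and 0.28 (0.5 / 0.6). The 5% critical value is 0.235 and the detectable r is 0.33. The best of 75 noise correlations would therefore look much like the effect that the study can detect.

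**Trying both correlation types.** If the better of Pearson and Spearman were taken on a single pair, the 5% error rate would rise to about 6.6%.

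**Power after adjustment** (r = 0.33, n = 70): Φ(√67 × atanh 0.33 − z), where √67 × atanh 0.33 = 2.81.
- Level 0.05: z = 1.96, power 80%
- Level 0.05/15: z = 2.94, power about 45%
- Level 0.05/75: z = 3.40, power 27-28%

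**The case against.** The strongest reply is that the plan never says that it will test 75 pairs. Section 5.3 is descriptive, the study is an observational cohort reported under STROBE, and the pilot may already have narrowed the variables. This stands in part: the 75 are possible pairs, not planned tests. But section 5.3.1 sizes the study for significance, the narrowed variables are not named, and nothing labels the analysis exploratory.

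A reader might also infer four stronger things that the documents do not support:
- That a false predictor is nearly certain. This needs near-independence, which is implausible for thresholds of the same kind at two sites or for overlapping questionnaires. The documents give no correlations, so only the range can be defended.
- That every pair will be screened by both Pearson and Spearman. Both are named only for the pilot-based sizing. Dual testing in the main analysis is a risk, not a stated plan, and it adds little.
- That 5% is the plan's level. No level is stated.
- That following the plan produces an invalid claim. The plan is silent on inference. It fails to prevent such a claim but does not prescribe one.

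**Conclusion.** The concern holds as an absence of any primary hypothesis or error control in a study sized for significance. At an assumed two-sided 5% and one 12-month analysis of about 15 × 5 pairs, about 3.75 false positives are expected if no association exists. The chance of at least one is about 43% to 98%. The lower end assumes correlations of 0.8 within both sets, and is still more than eight times the nominal 5% (0.43/0.05 = 8.6). The upper end assumes independence.

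A related risk is left open. Section 4.1 (Design) describes 30 pilot participants and 70 further patients, but does not say whether they will be pooled. If a measure that was picked because it looked promising in the pilot is then tested on data that include the pilot, selection bias remains even with one named pair.

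The plan should be changed. The defect can be repaired without altering the conduct of the study.

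**What to change.** Before the new patients' 12-month data are analysed, add to section 5.3:

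1. **One confirmatory test.** One pre-operative QST measure, chosen by the investigators from the pilot or on prior grounds and named in the text, as predictor of one 12-month outcome already collected (ODI is an example; the documents do not rank the scales). Use linear regression adjusted for the pre-operative value of that outcome, two-sided 5%.
2. **The analysis set.** If pilot results guided the choice of measure, run the confirmatory test in the 70 new patients only and give the pooled 100 as a secondary analysis.
3. **Everything else.** Label all other pairs exploratory, use Spearman throughout, adjust by Benjamini-Hochberg at 5%, and report every pair, whatever the result.

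This is wording only; no visit, measurement or patient is added. The confirmatory test keeps the full 5% level. The cost is power for the secondary pairs: for r = 0.33 at n = 70, it falls from 80% to about 45% at 0.05/15 and 27-28% at 0.05/75. Those are Bonferroni levels, so they are a lower bound for Benjamini-Hochberg. They also ignore dropout, for which the documents give no figure.

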4.1 Design

The experimental study design will be a prospective cohort study in accordance with the STROBE guidelines (31). A pilot-study including 15 male and 15 female participants have been conducted in order to assess the setup of QST and to evaluate if PET/CT were a viable way of identifying pain perception and potentially quantifying it. In accordance with previous protocol, data have now been reviewed and evaluated, leading to a modified setup with QST and a dismissal of PET/CT.

Based on the results gained from the pilot-study, it has been found reasonable to continue with further study participants in the QST-part of the study. Therefore, a continuance of QST measurements will be performed on further 70 patients as stated in detail below.

4.2 Study population

Study subjects will be recruited from patients assessed and found eligible for LDH surgery at Center for Spine Surgery and Research, Middelfart, part of the Department of Orthopedics, Vejle, Sygehus Lillebælt.

4.2.1 Inclusion criteria

- Informed consent
- Clinical and radiological indication for LDH surgery, assessed by an experienced spine surgeon
- Age 18-70 years
- No history of previous spine surgery
- No general contra-indication for spine surgery
- No psychiatric disorders requiring medication within the last 3 months

4.2.2 Exclusion criteria

- Psychiatric disorder that in the opinion of the investigators could impact the patient's ability to successfully complete the trial or otherwise interfere with outcomes
- Current malignant disease
- Current chemotherapy

- History of spinal fracture
- Hematologic disease
- Current pregnancy or breast-feeding (pregnancy-tested prior to inclusion)
- Chronic, generalized connective tissue disorders or chronic, non-specific pain disorders (fibromyalgia, whiplash (WAD I-V), etc.)

4.2.3 Subject withdrawal

- The patient has some other clinically significant medical condition that in the opinion of the investigators could impact the patient's ability to successfully complete the trial or otherwise interfere with outcomes
- The patient has, during the follow-up period, received medication or invasive intervention that in the opinion of the investigators could impact the patient's ability to successfully complete the trial or otherwise interfere with outcomes

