Furthermore, patients will undergo a Cold-Pressor Test (CPT) using a water-tub containing refrigerated water at 0-2°C in which they are to submerge their non-dominant hand to the wrist for 3 minutes. During the CPT, pain response will be monitored using a continuous VAS, controlled by the patient. For individuals who fail to tolerate the entire 3 minutes, time of withdrawal will be recorded. Immediately following the CPT, patients will, once again, be tested using the PPT described above. This is performed to analyze Conditioned Pain Modulation

(CPM) in the central nervous system. Following a short break (approx. 3-5 min.), patients will receive an injection of sterile hypertonic saline at the infraspinatus muscle of the scapula. Once again pain response will be measured using a continuous VAS.

	Pain Detection Threshold	Pain Tolerance Threshold	Pain Response	Continuous Pain Response	Complex Pain Modulation
Mechanical	PPT		PPT		PPT
Thermic		СРТ		CPT	СРТ
Chemical			NaCl	NaCl	

All patients participating in the study will undergo standard operative treatment, either open or microscopically, at Center for Spine Surgery and Research, Middelfart, and scheduled for an outpatient clinical control with a physiotherapist 4-6 weeks post-operative. The examination, assessment and treatment offered are not affected by study participation.

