5.3 Statistics

Data will be analyzed according to their type using STATA, i.e.; categorical data will be presented by means of frequencies and related percentages; continuous data will be displayed by means of descriptive statistics (mean, standard deviation, number of observations, minimum, median, maximum).

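### Section 4.2.3 lets investigators withdraw patients for treatment received after surgery, which risks outcome-related selection in the QST-outcome correlation

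*Combined protocol and SAP*

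**What the plan says.** Section 4.2.3 has two bullets, both resting on the investigators' opinion. The second concerns events after surgery: "The patient has, during the follow-up period, received medication or invasive intervention that in the opinion of the investigators could impact" the patient's completion of the study, or which could disturb the outcomes in some other way. It names no treatments and sets no threshold. The first bullet covers any other clinically significant condition, uses the same discretionary test and has no time limit. Withdrawal of consent is a separate matter, dealt with in section 7.

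Section 3 states the aim as whether "quantitative sensory testing (QST) of experimental pain responses can predict surgical outcome in patients with LDH". Its third question is "Is there a correlation between quantitative sensory testing of experimental pain responses and clinical outcome of surgery in LDH patients". On care, section 4.3 says "The examination, assessment and treatment offered are not affected by study participation".

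In the schedule at the start of section 5, ODI and SF-36 are collected before surgery and then only at 12 months. EQ-5D and the "DaneSpine questionnaire" have post-operative values at 6 weeks and 12 months. "VAS-leg and VAS-back" and the pain drawing are collected at 6 weeks, 6 months and 12 months. QST is repeated at 6 weeks and 6 months.

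Section 5.3 is descriptive: "continuous data will be displayed by means of descriptive statistics". It defines no analysis set and does not say how withdrawn patients or missing values are handled.

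**The concern.** Used as a baseline exclusion, such wording would only narrow the population. Applied after surgery, it conditions on events that are partly consequences of the outcome. Not all later medication or intervention reflects a poor surgical result, but with unrestricted care some of it will. That is an inference, though a modest one: section 2 puts unsatisfactory results at 10-40%.

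If withdrawn patients leave the analysis, the outcome distribution loses part of its poor end, where QST is meant to be informative. Selection on outcome alone pulls the correlation towards zero, beyond the loss of precision from fewer patients. Stopping follow-up before 12 months leaves ODI and SF-36 with no post-operative value, while the 6-week and 6-month measures may survive. And once these patients are gone, only an analysis without them is possible, so the effect of removing them cannot be checked.

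**Working it through.** **Inputs.** From the documents: a correlation as target (section 3); 70-100 patients, with Pearson and Spearman named (section 5.3.1); unsatisfactory results in 10-40% (section 2). Assumed: bivariate normality, two-sided 5% test, 80% power, complete removal of withdrawn patients, and withdrawal depending on outcome alone.

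**1. The plan's own figure.** The 70-100 cannot be reproduced, because section 5.3.1 gives no correlation, significance level, power or loss. Solving backwards, r = tanh((1.96 + 0.84)/√(n − 3)) gives 0.33 at n = 70 and 0.28 at n = 100. I take r = 0.33. With no loss, power is 80% from 70 patients and 92% from 100.

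**2. Effect on r.** Remove a share f of the worst 20% of outcomes. With cut-off c = 0.8416 and normal density φ(c) = 0.2800:

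- share kept: k = 1 − 0.2f
- mean of those kept: m = −fφ(c)/k
- variance of those kept: s² = [1 − f(0.2 + cφ(c))]/k − m²
- correlation in those kept: r′ = rs/√(r²s² + 1 − r²)

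For f = 1: s² = (1 − 0.4356)/0.8 − 0.350² = 0.583, so r′ = 0.33 × 0.764/√(0.109 × 0.583 + 0.891) = 0.258. For f = 0.5, s² = 0.845; for f = 0.25, s² = 0.933. Simulation of 4,000,000 pairs gives the same r′.

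**3. Power.** Power = Φ(atanh(r′)√(n′ − 3) − 1.96), where n′ is the number kept. For f = 1 from 70 patients, n′ = 56: 0.264 × √53 − 1.96 = −0.04, so 48%. Random loss of the same size: 0.343 × √53 − 1.96 = 0.54, so 70%.

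| Share of worst 20% withdrawn | Patients lost | r′ | Power from 70 (random loss) | Power from 100 (random loss) |
|---|---|---|---|---|
| 25% | 5% | 0.320 | 75% (78%) | 89% (91%) |
| 50% | 10% | 0.306 | 69% (76%) | 84% (89%) |
| 100% | 20% | 0.258 | 48% (70%) | 64% (85%) |

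The standard error of r at n = 70 is (1 − 0.33²)/√69 = 0.107, so the shifts of 0.01 and 0.02 in the first two rows are well inside sampling error.

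**4. Range.** From 70 patients, withdrawing half of the worst 10% or 40% gives r′ = 0.31 in each case, with power 72% or 65% against 77% or 70% for random loss. Withdrawing all of the worst 10% gives r′ = 0.28 and 61% against 75%. Withdrawing all of the worst 40% gives r′ = 0.22 and 29% against 57%.

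**5. Does keeping the patients always help?** The full-data Spearman correlation is 0.317. If later treatment leaves the outcome unchanged, analysing outcomes as observed recovers 0.317. If treatment resets the outcome to an unrelated value, Spearman becomes:

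| Who is treated | As observed | Exclusion |
|---|---|---|
| Worst 10% | 0.250 | 0.272 |
| Worst 20% | 0.217 | 0.246 |
| Marker correlated 0.7 with outcome, 10% | 0.269 | 0.296 |
| Same, 20% | 0.238 | 0.285 |
| Marker correlated 0.5, 10% | 0.277 | 0.307 |
| Same, 20% | 0.247 | 0.301 |
| Marker correlated 0.3, 10% | 0.282 | 0.313 |
| Same, 20% | 0.250 | 0.311 |

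Under a full reset, exclusion is nearer 0.317 in all eight rows. In the worst-20% row, power from 70 / 100 patients is 44% / 58% as observed and 44% / 60% by exclusion.

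**The case against.** The strongest objection is that the remedy may not deliver the full-data benchmark. Step 5 bears this out: if later treatment changes the outcome, as-observed values can be more attenuated than exclusion. That stands, and it limits the claim to the value of being able to show both analyses.

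Second, the effect is small in any moderate case, and nothing in the documents suggests near-complete withdrawal of poor-result patients. That also stands.

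Third, the bullet does not make every later treatment a ground for withdrawal. It applies only where completion or the outcomes could be affected. This narrows the rule but does not remove the risk, since treatment for a poor result is the kind most likely to be judged to affect outcomes.

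Fourth, the bullet may be meant to protect the repeat QST from recent medication. That aim is legitimate, but flagging the affected measurements meets it without losing the patient.

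Fifth, the wider gap is section 5.3, which defines no primary QST variable, outcome, time point or inferential method. This is true, and extra analyses add to the number of comparisons. But 4.2.3 is a stated rule that can remove data, and a fuller analysis section could not restore data never collected.

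**Conclusion.** The concern holds as a risk. The second bullet permits discretionary withdrawal for events partly caused by the outcome under study, and no available text keeps those patients in follow-up or analysis. Under the stated assumptions the distortion is small if up to half of the poor-result patients are withdrawn, and material only if nearly all are.

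A reader might infer more than the documents support:

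- That the correlation will be biased by a known amount. No r and no withdrawal rate are given, and the 10-40% is a rate of unsatisfactory results, not of withdrawal.
- That the bias must be towards zero. This follows only for selection on outcome alone. If withdrawal also tracked QST, the direction could differ, though nothing shows that it does.
- That withdrawn patients are certainly dropped. The text is silent; if they were followed and analysed, the problem would not arise.
- That keeping everyone is always less biased. Step 5 shows otherwise.

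**What to change.** Amend section 4.2.3 so that neither treatment received during follow-up (second bullet) nor a condition arising after surgery (first bullet) is by itself a reason to stop study follow-up or discard data. Changing only the second would leave the same discretion available under the first.

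Then:

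- follow every consenting operated patient to 12 months at the visits already scheduled, and keep all data collected;
- record later medication and interventions with dates, and flag repeat QST measurements that they may affect;
- report the number, timing and reasons of any withdrawals;
- report the QST-outcome correlation in all followed patients and, beside it, an analysis excluding a stated category of later treatment, saying whether medication alone counts;
- optionally, add a rank analysis that gives the worst rank to patients with further spine intervention.

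The cost is protocol wording, some extra data recording and one or two extra analyses, with no added visits or patients. The downside is that as-observed outcomes carry the effect of later treatment. Clinical care and the right to withdraw consent are unchanged.
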